**3 \* Describe the relevant prior experience and gaps in current knowledge. Describe any relevant preliminary data:**

As the number of exomes and genomes sequenced grows, so does the potential for detecting clinically significant mutations in seemingly healthy individuals as secondary findings. A 'clinically significant,' or 'clinically actionable,' mutation is one for which there is a strong body of evidence that preventative action could be taken in mutation carriers to markedly reduce the risk of disease. The American College of Medical Genetics (ACMG) has identified a panel of 59 genes associated with highly penetrant genetic disorders that they consider to be clinically actionable if they harbor deleterious variants.

Recently, the Amish Complex Diseases Research Program of the University of Maryland identified a mutation (deleterious gene change) in the KCNQ1 gene, a gene known to cause Long QT Syndrome (LQTS). LQTS is associated with an increased risk of fainting (syncope) and sudden death. Beta blocker medications have been shown to reduce the risk of syncope and sudden death in LQTS by 70-90%. Therefore, identifying a mutation known to cause LQTS can lead to treatment that significantly reduces an individual's risk of serious cardiac events.

In the Old Order Amish community, the KCNQ1 variant is enriched over 100,000-fold compared to other populations. We identified 140 KCNQ1 Thr224Met carriers among our Amish Complex Disease Research cohort in whom whole exome or whole genome sequencing was performed for research purposes. These individuals were generally healthy and participated in research studies involving cardiometabolic health carried out in the Old Order Amish community of Lancaster, Pennsylvania.

With consultation from the IRB, we sent letters to these carriers describing that we had identified an apparent genetic variant that could impact their health and asked if they would like to have the genotype clinically confirmed and receive clinical evaluation. Of the 134 individuals who were mailed letters to date, 88 responded that they would like confirmation and evaluation. 16 individuals responded that they did not want to receive the results, and the remainder did not respond.

To date, 88 individuals have participated in a return of results study (ROR) for clinical confirmation of the mutation, collection of clinical information, genetic counseling, and recommendations for treatment. Genetic counseling included recommendations for all first degree relatives (who are at 50% risk of having the KCNQ1 mutation) to undergo genetic screening (cascade testing). This testing would involve going to the Clinic for Special Children and obtaining the genetic test via a blood sample for \$50 per test.

Cascade testing is considered to be a highly efficient procedure for identifying additional mutation carriers who might be helped through a preventive intervention. Despite the very clear potential clinical benefit of cascade testing, uptake has traditionally been low, particularly in the United States where active screening (i.e. direct contact of relatives) is not allowed due to privacy laws.

Understanding the impact of returning these results and initiating cascade screening of family members is critical for developing best practices and optimizing the processes. Most cascade screening studies to date have been conducted outside the United States where different laws exist regarding contacting family members. Therefore, our study will attempt to address a gap in knowledge regarding whether overcoming physical and financial barriers will improve uptake of cascade screening.

**4 \*Provide the scientific or scholarly background, rationale, and significance of the research and how it will add to existing knowledge:**

Despite the very clear potential clinical benefit of screening family members of carriers to identify and counsel family members of carriers, uptake of cascade testing has traditionally been low, particularly in the United States where active screening (ie direct contact of relatives) is not allowed due to privacy laws. A study of hypertrophic cardiomyopathy found a 39% uptake of genetic counseling and testing among family members of a proband with a pathogenic mutation. Similar rates have been seen in breast cancer, and hereditary nonpolyposis colorectal cancer with update rates of 23-45%. As disease causing mutations are discovered more commonly, the investigation of the ELSI impact of this screening is paramount with greater numbers of individuals will requiring pharmacological treatment and having knowledge of their (or their children's) increased risk of sudden death. This question is particularly important with diseases with incomplete penetrance, such as LQTS. Identifying methods to increase the palatability of cascade screening within families is a high priority need.

We propose to conduct our study in the context of the Lancaster Amish, a population isolate. While there is a temptation to regard this as a limitation in terms of generalization to broader populations, this view fails to consider the magnitude of the problem in population isolates where deleterious actionable variants are most likely to be highly enriched, and frankly, where personalized medicine is most commonly practiced. We have identified 140 carriers of the KCNQ1 rs199472706 variant, and given the large family sizes of the Amish (7-8 offspring on average), this represents a huge additional pool of carriers who could potentially benefit from screening. In other words, there is a very large and disproportionate public health burden in isolate populations like the Amish (e.g., Ashkenazi, Mennonite, Hutterite, Sardinian, Icelandic, and Finnish, among others) for which population-specific screening interventions are sorely needed. As an aside, we certainly expect that lessons learned about cascade implementation in the Amish will be relevant to many other communities and populations, not just population isolates.

ID: V1EW4E02805EA0C00  
Name: v2\_Justification, Objective, & Research Design

HP-00081981

Supporting Literature\_V2

## Supporting Literature

1 \* Provide a summary of current literature related to the research: ***If you uploaded a separate research protocol document in the 'Research Protocol' page, cite the applicable section and page numbers from that document in the answer box below.***

See pages 44-50 of attached grant for summary of current literature.

2 If available, upload your applicable literature search:

Name	Created	Modified Date
 Uptake of genetic testing in cardiomyopathy(0.01)	8/14/2018 2:02 PM	8/14/2018 2:02 PM
 Genetic testing in channelopathies and cardiomyopathies(0.01)	8/14/2018 2:00 PM	8/14/2018 2:00 PM
 ACMG 59(0.01)	8/14/2018 1:58 PM	8/14/2018 1:58 PM

ID: ViEW4E02805A7E400  
Name: v2\_Supporting Literature

HP-00081981

Study Procedures\_V2

## Study Procedures

**If you uploaded a separate research protocol document in the 'Research Protocol' page, cite the applicable section and page numbers from that document in the answer boxes below. (If this study is a collaborative UM/VA study please list each procedure that is being conducted and the locations where it is being conducted.)**

1 \* Describe all procedures being performed for research purposes only (these procedures would not be done if individuals were not in the study) and when they are performed, including procedures being performed to monitor subjects for safety or to minimize risks:

Individuals who participated in the KCNQ1 ROR study (probands) and their first degree blood-related family members will be invited to participate. All probands will be mailed an information / consent letter with a response form (uploaded in Informed Consent Section), a questionnaire about their attitudes and experience with genetic testing (uploaded to Surveys Section), and a sample family invitation letter (uploaded to Recruitment Section). In the consent letter, probands will be asked to complete and return the questionnaire as an indication that they agree to join the study. They will be informed that they may be asked to participate in an in-person interview. The letter will also ask if we can invite their adult first-degree family members who live locally to take part in the study, whether or not the proband participates. They will be given the option to enroll their minor children (with appropriate consent and assent) in the free cascade testing portion of the study. The proband will complete and return the response card to indicate whether they agree to contact of family members.

With the proband's permission, the family invitation letter will be mailed to the first-degree family members of the proband who live locally, using information from the 2009 Fisher Book and 2018 Address book of the Lancaster County Amish. At the proband's request, copies of the family invitation letter will, instead, be mailed to the proband so they can hand deliver them to family members of their choosing.

In the invitation letter, family members will be asked to take part in a study involving screening for the KCNQ1 variant, including any or all of the following: provide a saliva sample to check for the KCNQ1 genetic variant at no cost to them, complete a questionnaire about their attitudes and experience with genetic testing, and possibly take part in an in-person interview. They will be instructed to return a response form or call the Amish Research clinic if they are interested in participating in the study.

Family members who indicate, by returning the response card or by phone call, that they are interested in participating in the free genetic testing will be visited in their home by a study team member and an Amish liaison. Initial interactions are described in the Recruitment Section. For those who are interested in participating, informed consent will be obtained from adults and parents of minor children. Written assent will be obtained from minors aged 13-17; verbal assent will be obtained from children 7-12 years of age. Consent and assent will be obtained prior to any study procedures are performed. The informed consent process is detailed in the Consent Section of this application. Participants/parents will be asked to complete a questionnaire including demographics, medical and family history, and medications (uploaded in.

### Sample Collection and Processing:

A saliva sample will be collected from each participant. DNA will be used for clinical testing for the KCNQ1 Thr224Met variant and an aliquot will be stored for possible future genetic analyses. Saliva samples will be collected from adults and children who are able to provide sufficient saliva volume for testing. For small children and infants, mouth swabs will be used to collect saliva.

Participants should not eat, drink, smoke or chew gum for one hour prior to collection of saliva. For saliva, participants will be asked to expectorate approximately 2 mL of saliva in an Oragene DNA (DNA Genotek, Ontario, Canada) saliva collection kit. For small children and infants, a swab will be used to collect saliva. The swab will be placed in oral cavity and sample will be collected from the right and left side of the cheek by rotating the swab 10 times in up and down motion on each side. The swab will be placed in collection container. All samples will be stored at ambient temperature until transport to the receiving laboratory.

Clinical genetic test results will be returned to the participant by a genetic counselor [MOD 6: and/or study team member. Individuals who are tested for the risk allele (positive or negative) will also be offered an electrocardiogram (ECG) along with information regarding appropriate medical follow-up, recommendations for treatment, and recommended testing of first-degree relatives.] along with information regarding appropriate medical follow-up, recommendations for treatment, and recommended testing of first-degree relatives. After they have received their KCNQ1 results, participants who agreed to take part in the survey portion will be mailed a questionnaire about their attitudes and experience with genetic testing. If the family member only agrees to completing a survey (not the KCNQ1 testing), a family information / consent letter (uploaded to Surveys Section) in the Additional documents Section) and a questionnaire will be mailed with instructions for completion and return.

Probands who indicate that they want genetic testing for their minor children who live at home will be contacted to set up an appointment for testing as described above. Minor children will not complete the survey or interview portions of the study.

Stamped and addressed envelopes will be provided for all return mailings.

A subset of participants will be asked to take part in a 1-2 hour face-to-face in-depth interview. Those who have agreed to an interview will be visited at their home by a study team member and an Amish liaison to complete the interview. The interview will be audio recorded so that it can be transcribed and analyzed.

2 \* Describe all procedures already being performed for diagnostic or treatment purposes (if not applicable to the study, enter "N/A"):

N/A

3 \* Describe the duration of an individual participant's participation in the study:

Study duration is dependent on which portions of the study the individual participates. Duration from receipt of the letter through the final questionnaire could span 1 1/2 years

4 \* Describe the amount of time it will take to complete the entire study:

2 years

5 \* Describe any additional participant requirements:

N/A

ID: VIEW4E0280585B400  
Name: v2\_Study Procedures

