Aim 1: Prior to the start of our intervention, all probands will be mailed a consent letter describing the study, a questionnaire, a response card and a copy of the family invitation letter. The questionnaire will capture data on the period of time since their return of results, including, the extent to which they shared results with family members, health behaviors (i.e. are they taking preventative therapy, if indicated) and how the results have impacted them. With the proband's permission, invitation letters will be mailed to their first degree relatives to offer study participation including the intervention (free, in-home, saliva-based genetic testing) and completion of questionnaires about their experiences with genetic testing. The proband can decide to enroll their minor children who still live at home in the cascade screening (Screening only for children under age 18 with specified consent/assent). We will offer the intervention for approximately 9 months, then we will repeat the mailed questionnaires assessing uptake, disclosure, health behaviors, and general impact of the intervention.

We will compare outcomes before the implementation of our intervention (the 'traditional' cascade screening period) and after (the 'simplified' cascade screening period). Our primary outcome addresses the question of whether our simplified cascade screening intervention improves uptake of screening. Our secondary outcomes assess whether, with access to simplified screening (1) probands will tell more family members, who may or may not choose to get screened, (2) informed family members are more likely to get tested, and (3) identifying more individuals with the KCNQ1 variant actually results in more beta-blocker prescriptions since the Amish typically take very few prescription medications. The tertiary outcomes are demographic characteristics associated with uptake of cascade screening or uptake of preventative therapy.

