## Surveys/Questionnaires

You indicated that this study involves surveys and/or questionnaires.

If you uploaded a separate research protocol document in the 'Research Protocol' page, cite the applicable section and page numbers from that document in the answer boxes below.

1 \* List all questionnaires/surveys to be used in the study, including both standardized and non-standardized assessments:

Baseline Proband questionnaire  
 Post-intervention Proband questionnaire  
 Post-intervention mutation negative Family Member questionnaire  
 Post-intervention mutation positive Family Member questionnaire  
 Family Member declined testing questionnaire  
 Medical, social, and family history questionnaire  
 Medication form

2 \* Upload a copy of all questionnaires/surveys:

Name	Created	Modified Date
 Family positive(0.03)	11/8/2018 1:53 PM	5/16/2022 11:33 AM
 Family negative(0.03)	11/8/2018 1:51 PM	5/16/2022 11:33 AM
 Family no testing(0.02)	2/3/2019 7:31 PM	5/16/2022 11:33 AM
 Medication Flow Sheet.docm(0.01)	2/4/2019 12:18 PM	2/4/2019 12:18 PM
 Medical, Social, and Family history form(0.01)	2/4/2019 12:17 PM	2/4/2019 12:17 PM
 Proband baseline(0.03)	9/13/2018 4:06 PM	2/3/2019 7:28 PM
 Proband followup(0.02)	11/8/2018 1:48 PM	2/3/2019 7:27 PM

3 \* What is the total length of time that each survey is expected to take?

20 minutes

4 \* Are any of the questions likely to cause discomfort in participants or cause harm if their confidentiality were breached? (i.e., Illegal activities)

Yes  No

5 \* Do any questions elicit information related to the potential for harm to self or others?

Yes  No

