### **B1.2 Secondary outcomes**

- a. Extent of disclosure of genotype results before and after the intervention. This outcome is defined as the number of family members (siblings and children) told (reported via survey) out of the total number of proband first degree relatives (known from the Fisher Book and asked on the survey).
- b. Proportion of informed first-degree relatives who get screened before and after the intervention. This outcome is defined as the number of family members tested out of the number told by probands (reported via surveys)
- c. The overall rate of uptake of preventative therapy among probands and family members (e.g., see a cardiologist and/or take a beta-blockers)

Analyses of secondary outcomes (a) and (b) will occur in the same manner as the primary outcome, by comparing proportions before and after the intervention. For secondary outcome (c), we don't expect the proportion of appropriately treated carriers to be impacted by our intervention, but rather the absolute number of treated individuals would be impacted by detecting more carriers with improved cascade screening. For the disclosure outcome (a), we will compare results using the denominator based on Fisher book data and based on data reported in the survey. For the uptake of screening among those informed outcome (b), the denominator is based on the survey results (the proband will be asked who they disclosed results to and the family member will be asked if their family member told them). For the uptake of clinical recommendation outcome (c), we will use data from the participants' charts to determine whether beta-blocker therapy was indicated and prescribed. We will gather data from the survey on whether participants are following the recommendations. While we don't expect our intervention to change the proportion of individuals appropriately treated, we will compare the proportions before and after the intervention to confirm this assumption.

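### The preventive-therapy outcome has no common time since result, so its before/after proportions cannot confirm that treatment uptake is unchanged

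*Combined protocol and SAP*

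**What the plan says.** SAP B1.2 defines outcome (c) as "The overall rate of uptake of preventative therapy among probands and family members", with seeing a cardiologist and taking a beta-blocker as examples. It states no time point. Two sources feed it. Charts show whether a beta-blocker was indicated and prescribed, and the survey shows whether people follow the advice. No chart cut-off date is given. The plan expects the number of treated carriers to grow and the proportion to stay put, and adds that "we will compare the proportions before and after the intervention to confirm this assumption". The protocol's Sample Size and Data Analysis section repeats this.

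Timing comes from elsewhere in the protocol:

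- **Probands.** For the baseline form, the research design section (Aim 1) says: "The questionnaire will capture data on the period of time since their return of results". All of them had received results before the offer.
- **Tested relatives.** Study Procedures says: "After they have received their KCNQ1 results, participants who agreed to take part in the survey portion will be mailed a questionnaire". It gives no interval.
- **Close of the offer.** Aim 1 says: "We will offer the intervention for approximately 9 months, then we will repeat the mailed questionnaires assessing uptake, disclosure, health behaviors".
- **Forms.** Surveys/Questionnaires lists a baseline and a post-intervention form for probands, and one form for carrier relatives, the "Post-intervention mutation positive Family Member questionnaire".
- **Length of participation.** "Duration from receipt of the letter through the final questionnaire could span 1 1/2 years".

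**The concern.** Seeing a cardiologist and starting a drug both follow the result and take time. A treated proportion therefore depends on how long people have known their result, as well as on what they choose to do. The plan compares a baseline proportion made up mostly of probands with a later one that adds newly found relatives, and reads equality as confirmation that uptake is unchanged. If time since result differs between the two readings, that inference fails.

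The count is affected too. The protocol asks whether finding more carriers leads to more beta-blocker prescriptions. A relative whose result is recent may be counted as untreated simply because there has been no time to act. The study could not then separate carriers who decline treatment from carriers not yet followed long enough.

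**Working it through.** **Figures in the plan.** The documents give no number for outcome (c). Their screening example is used here only to size the group of new carriers. It reproduces: 500 − 15 = 485, and 0.18 × 485 = 87.3, stated as 87. At the stated 50% carrier risk, 87 × 0.5 = 43.5 new carriers. The protocol has 88 probands (the SAP says 70).

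**Elapsed time.** When the offer closes at about month 9, every proband is at least 9 months past the result, and every relative tested under the offer is at most about 9 months past it. A mailing triggered by the result leaves relatives less time still. A chart review on one calendar date keeps the same gap.

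**Illustration with unchanged behaviour.** Assumptions that the documents do not supply:

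- Carriers act at a constant rate, with half having acted by 12 months: h = ln 2 / 12 = 0.0578 per month. The proportion who have acted by t months is C(t) = 1 − exp(−ht).
- Relatives' results are spread evenly over 9 months and read at month 9.
- The baseline group is probands only. The few carriers found by traditional testing are left out.
- Probands are read again 9 months after baseline.

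Relatives: 1 − (1 − exp(−9h)) / (9h) = 1 − 0.4054 / 0.5199 = 0.220.

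Pooled after-proportion: [88 × C(t + 9) + 43.5 × 0.220] / 131.5, where t is the probands' time since result at baseline.

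| t (months) | Before, C(t) | Probands after, C(t + 9) | Pooled after | Apparent change |
|---|---|---|---|---|
| 6 | 0.293 | 0.580 | 0.461 | +16.8 points |
| 12 | 0.500 | 0.703 | 0.543 | +4.3 points |
| 18 | 0.646 | 0.790 | 0.601 | −4.5 points |
| 24 | 0.750 | 0.851 | 0.643 | −10.7 points |

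The sign changes at about 15 months. If the share acting by 12 months is 30% or 70% instead of 50%, it changes at about 17.5 or 12 months. With 70 probands and the 50% rate, the change is +1.8 points at 12 months and −14.1 at 24.

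**If proband uptake has already levelled off.** Let p be the final treated proportion, and suppose relatives have reached half of their eventual uptake when read. The pooled proportion is (88p + 43.5 × 0.5p) / 131.5. It is 0.250 for p = 0.3, 0.417 for p = 0.5 and 0.584 for p = 0.7. These are falls of 5.0, 8.3 and 11.6 points. If relatives are read late enough to have reached full uptake, the fall is zero. For p = 0.5 a rise of about 12 points in proband uptake would cancel it.

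**Number treated.** Under the constant rate, 43.5 × 0.220 = about 10 new carriers count as treated at month 9. The same people would give 43.5 × 0.5 = about 22 at 12 months. Unlike the pooled proportion, this count can only be pushed down.

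**The case against.** A reader might infer that the treated proportion will show a false fall after the intervention. The documents do not support that. Proband follow-up lengthens between the two surveys as well, and the table shows a rise when probands are fairly recent. The existing-data range, October 2015 to October 2018, covers several source protocols and gives no individual return-of-results dates, so follow-up of years for probands is an inference.

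A reader might also infer that carrier relatives are surveyed once, almost immediately. The form list and the result-triggered mailing point to a single survey, but that mailing comes at an unstated time after the result, the form is labelled post-intervention, and the questionnaires are repeated after about 9 months. The timing is open.

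Prescription status comes from charts, so the survey date limits only the adherence part, and charts could be read late in a two-year study. That is fair. But no cut-off is set, and a common calendar date keeps elapsed time unequal. A late reading helps only if uptake has levelled off by then.

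The constant rate is a choice of shape. Advice is given with the result, so early uptake followed by a plateau is plausible, and the gap would then be smaller. Finally, this is a pilot, (c) is secondary, the proportion is a check on an assumption, and undercounting the number treated errs on the cautious side. These points limit the weight of the problem but do not make the two proportions comparable.

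**Conclusion.** The point holds as a lack of comparability, with no predicted direction for the pooled proportion. Outcome (c) has no common window since result and no chart cut-off, and its two readings differ in composition and follow-up. With no change in behaviour the pooled proportion can move either way: about +4 points with probands 12 months past their result at baseline and about −11 points at 24 months, under the assumed constant rate and 88 probands with 43.5 new carriers. Agreement or disagreement between the two proportions is therefore not evidence about whether uptake changed. For newly found carriers the number treated is biased downward whenever uptake takes time. The actual size depends on proband result dates, the mailing interval, the chart date and the speed of uptake, none of which the documents give. The primary outcome is unaffected, and the correction is a cheap improvement.

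**What to change.** - Define (c) at one fixed time since each person's own result, the same for probands and relatives. Six months is an example; the team should choose and state the value.
- Read prescription status from charts at that elapsed time in both groups. This needs the result date and the prescription date for each person.
- Mail carrier relatives the health-behaviour items at that time.
- Report probands and relatives separately, and count treated carriers only among those who have reached the time point.
- Treat survey-reported adherence in probands as descriptive. Their baseline form covers the whole period since results, so adherence at a fixed earlier time cannot be recovered from it.

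The cost is a later mailing or one extra short one, some SAP wording, and a readout of (c) some months after the offer closes. With the six-month example, a result at month 9 is read at 9 + 6 = 15 months, inside the 18 months that the protocol already allows for a participant. Only the timing of measurement changes.
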